Protocol

1. Project Title

Effects of Aging on Cortical Excitability During Motor Learning

(Short title: Aging and Cortical Excitability)

2. Investigators:

Principal Investigator: [name]

Co-Investigators: [name]

[name], MS

Version Date: 08/30/2022

3. Abstract:

Aging is associated with changes in brain excitability that has direct impacts on behavior. Brain excitability is modulated by either selective increases in firing rates (excitation) or selective decreases in firing rates (inhibition). Our brains maintain cortical function by balancing excitability with inhibition largely through inhibitory interneurons that use the neurotransmitter gamma aminobutyric acid (GABA). It is currently unknown if total GABA levels in the brain increase or decrease as a function of age, but recent studies have shown that GABA can be selectively modulated during cortical processing including motor learning. That is, GABA levels change during selective engagement in repetitive task practice (Floyer-Lea et al., 2006) and this change is related to functional performance (pilot data). Specifically, in younger adults, GABA levels tend to decrease during the entrainment of a motor task and return to baseline when the task is performed automatically. This selective decrease in GABA levels is consistent with long term potentiation, as cortical excitability is acutely increased with the reduction in GABA. These data have been shown in younger adults, however, little is known about the function of GABA during motor learning in older adults. This is particularly important because behavioral neuroplasticity is dependent on training induced changes in cortical excitability likely mediated by alteration of GABAergic function. We do know that older adults learn motor tasks at a much slower rate and with greater errors than younger adults (Salthouse, 1996). Interestingly, our pilot data show that GABA levels increase during this errorful learning phase in training with aging adults. The cause of this increase is yet unknown and unconfirmed. The purpose of the current project is to attempt to understand changes in the aging brain respective of motor learning by focusing on the neural mechanisms responsible for changes in cortical excitability states. Importantly, we expect that there are individual differences in performance in aging adults as has been reported widely in previous literature (D'Esposito & Aguirre, 2003). We will employ magnetic resonance imaging, magnetic resonance spectroscopy, transcranial magnetic stimulation and behavioral testing to attempt to quantify the neural factors associated with GABAergic function that may account for individual differences in skill acquisition and retention. Interestingly, aerobic exercise has been shown to improve motor skill performance and learning performance in older adults (McGregor et al., 2018). To test the potential mechanism of how aerobic exercise changes cortical excitatory balance, we will be randomizing participants into either a 12-week aerobic exercise (cycling) or a balance and stretching condition. Aerobic exercise is believed to increase blood flow, increase neurotrophic factors and increase metabolic efficiency at the cellular and receptor level. Using transcranial magnetic stimulation and magnetic resonance imaging and spectroscopy, we will test the effects of exercise on both GABA levels and receptor function in conjunction with measuring levels of serum neurotrophic factors and cardiovascular response. The current project represents a considerable leap forward in terms of combining leading edge neurophysiological techniques in a human model to understand the mechanisms responsible for aging-related changes in motor performance and in future work, rehabilitation of disease. This has strong implications to rehabilitation after motor pathology, as most motor diseases affect the aged brain. By understanding the mechanisms of learning in this age cohort,

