Recently, in collaboration with magnetic resonance physicists at Georgia State University and Emory University, we have successfully gained the capability to acquire MRS data using a vetted MRI sequence called MEGA-PRESS. We will utilize this sequence during the present study to answer the question of how much GABA per unit volume exists in posterior cingulate and primary motor areas of the brain, two regions previously shown to evidence tonic levels of GABA at rest. We now have the capability to use magnetic resonance spectroscopy to index the amount of GABA present in a given area. As such, this is a great leap forward for our capabilities to assay the function of the central nervous system as we can now link GABA levels in the brain with both behavioral performance and regional task activity during functional MRI. The effect of aging on the quantity of GABA in the central nervous system, particularly in the motor cortex is currently unknown. In the current project, we will be measuring GABA levels using MRS during a motor sequence learning task, which has been shown to modulate GABA levels in younger adults. Importantly, we will also be acquiring MR measures of cortical glutamate-GABA metabolism using a MRI sequence called glucoCEST. This affords us the capability of indexing the energy exchange within the brain. With the assistance of [name], PhD, we will also be indexing energy metabolism in skeletal muscle. Specifically, participants will be repositioned in the MRI magnet after a short break and we will then acquire Phosphorus-31 MRS of the quadriceps. These

data will be correlated to data from the cortical acquisition using the glucoCEST sequence. Importantly, these data will give us an index of muscular energy metabolism (production of adenosine triphosphate) prior to and after engaging in a 12-week exercise program that has been shown repeatedly to increase oxygen metabolism (Nocera et al., 2017; McGregor et al., 2018). As an exploratory aim, we will relate the changes in glucoCEST metabolism within the brain with changes in muscular energy capacity. We believe this is the first project to ever acquire such data.

Transcranial Magnetic Stimulation

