From the cited findings and the PI's previous research program, the impetus behind the PI's current research program has evolved. A previous study compared the effects of long-term physical fitness on neurophysiological measures of interhemispheric inhibition that may be diagnostic of biological motor health. This study has shown that elderly adults who are physically fit may mitigate a loss of interhemispheric inhibition prevalent in sedentary older adults (McGregor et al., 2011; 2013). Moreover, an aerobic exercise intervention was effective in increasing the duration of the ipsilateral silent period while improving motor performance (McGregor et al., 2018). We believe this was the first study to show that an aerobic exercise intervention has direct effects on TMS measures of cortical excitability. However, we do not yet have data as to the mechanism causing these changes. The present study seeks to address this gap in knowledge by integrating leading edge MRI/MRS, TMS, behavioral and bioassay techniques to improve our understanding of how exercise changes neurochemical, metabolic and intracortical patterns of activity associated with motor learning.

5. Specific Aims:

Specific Aim 1) To determine the relationship of motor performance on two different measures of cortical inhibition (TMS and MRS).

GABA levels in left primary motor areas will be lower in older adults who perform more poorly on upper extremity behavioral assessments.

Specific Aim 2) To determine the effect of an aerobic exercise regimen on motor learning and related GABA concentration changes using MRS.

Aging-related changes in GABA function can be mitigated with an aerobic exercise intervention.

Specific Aim 3) To determine the effects of motor learning prior to and after an aerobic exercise intervention on GABA receptor function using TMS.

Motor learning will modulate cortical inhibition at the receptor level causing decreased intracortical inhibition, but preserved interhemispheric inhibition. Older adults that are enrolled in the regular aerobic exercise will show maintenance or enhancement of interhemispheric inhibition and increased GABA efficiency during motor learning resulting in increased modulation of GABA receptors.

Specific Aim 4) To compare measures of cortical energy metabolism with measures of skeletal muscle metabolism using MRI and MRS measures prior to and after an aerobic exercise intervention.

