Maximal Treadmill Exercise Test: Unless contraindicated, participants will undergo maximal exercise testing using an exercise protocol validated for this purpose (e.g., Bruce, Balke, or similar, or using a ramp protocol). Participants will progress through a gradual increase in work rate based on the specific protocol being used until they either become fatigued and decide to stop, develop other symptoms that prohibit further exercise (e.g., musculoskeletal pain), or there is an absolute indication for termination of exercise testing (Table 2). Vital signs, including blood pressure and heart rate, will be recorded at regular intervals throughout the test, and participants will be monitored with continuous electrocardiography. Participants may also be asked to report their rate of perceived exertion (RPE) at various points during the test. After testing, participants will be monitored until their heart rate and perceived exertion have normalized. A registered nurse (RN) or exercise physiologist (EP) will be present for the test duration.

Participants will be randomly placed in an aerobic exercise intervention or a stretching control intervention.

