Interval Exercise Group: For 12-weeks participants will engage in progressive whole body stretching, toning and balance exercises designed for individuals 60 years and older. Participants will meet for the same total duration time as the aerobic exercise group. Heart rate will be monitored to ensure participants maintain exercise levels below aerobic training zone.

Remote Exercise Monitoring: As an alternative, participants that are uncomfortable with receiving face-to-face training within the hospital will be given the option to continue their exercise intervention visits remotely. For participants that have been randomly assigned to the 'spin' exercise training program, will be provided a stationary cycle ergometer that has been sanitized properly to use during the 12-week period. All subjects will be monitored and trained through VA and Emory approved remote access sites.

Control Group: A random subset of participants will be in a 12-week wait-list control. These participants will undergo the same pretesting procedures as described above. After 12-weeks of no activity with the study team, these participants will return and repeat the pre-assessment, 12-week exercise intervention and post assessment as described above.

3. Electronic Activity Data: Electronic activity data will be generated by Apple Watches functioning in two possible modes. Each mode has unique requirements for data security. The Watch will collect the participants' daily total activity level.

1. *Stand-alone.* Some Apple Watches loaned to participants will be paired with VA-furnished iPhones. When not loaned out to participants, these iPhones will remain at the VA in a locked and secure environment (12C-173b). Because the watches will be functioning at a remote location, they will be unable to sync the data they generate to an iPhone or a network cloud. Instead, our team has written code to preserve this data in formatted files on the watch until the watch is returned to our possession. The data stored on passcode protected Apple Watches is secured with AES-256 encryption.

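### The random wait-list 'Control Group' has no stated size and no explicit place in the two-arm randomisation, and its path of at least 24 weeks exceeds the stated 4-month maximum

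*Combined protocol and SAP*

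**What the plan says.** All references are to the combined protocol and SAP.

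- **Randomisation.** The abstract (section 3) states: "we will be randomizing participants into either a 12-week aerobic exercise (cycling) or a balance and stretching condition". Section 6, just before the intervention descriptions, agrees and names the control: "Participants will be randomly placed in an aerobic exercise intervention or a stretching control intervention".
- **Numbers.** Section 9 recruits 40 older adults, plus a separate younger comparator group for the MRI scans. Section 10 needs 20 per group and allows up to 8 additional older participants to cover dropout.
- **Labels.** The stretching programme is then described under a different name: "Interval Exercise Group: For 12-weeks participants will engage in progressive whole body stretching, toning and balance exercises". The control label is used for something else: "Control Group: A random subset of participants will be in a 12-week wait-list control".
- **Wait-list path.** Wait-listed participants are pretested and have 12 weeks without study activity. Then "these participants will return and repeat the pre-assessment, 12-week exercise intervention and post assessment as described above".
- **Duration.** The Study Visits paragraph in section 6 gives a maximum of 4 months for participation and makes no exception. It refers to a visit table that is not in the available text.
- **Sample timing.** Section 7 (Blood Draw) places all blood and saliva collection at weeks 1 and 12.

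The wait-list appears in no other part of the available text: not in the abstract, the aims or the sample-size section.

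**The concern.** Two things in the text do not fit together.

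First, the word control names two different groups: the stretching arm in one paragraph and a no-activity wait-list in another. The wait-list subset is random, but the plan does not say how many people it takes, when they are drawn, or whether they are drawn instead of, or in addition to, the aerobic-or-stretching allocation. A comparison of aerobic exercise with stretching and a comparison with no activity answer different questions. Whoever prepares the allocation list has to guess how the wait-list fits in.

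Second, the stated length of participation does not cover the wait-list path. That leaves a stated figure wrong for every wait-listed person. It also leaves open whether a week-12 sample is taken after exercise or at the end of the wait.

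**Working it through.** **1. The plan's own figures.** Two arms of 20 (section 10) make 2 x 20 = 40, which is the number of older adults in section 9. Nobody is left for a third group unless the arms shrink or the dropout reserve is used.

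Section 10 links 20 per group to an effect size of about .83 but gives no alpha, sidedness or power. Assuming a two-sample t-test, alpha .05 and 80% power, 20 per group detects d = .91 two-sided or d = .80 one-sided. The .83 lies between these, so it can be neither confirmed nor refuted from the document. Nothing below depends on it except the illustration in step 4.

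**2. Which programme follows the wait.** The wait-list paragraph (quoted above) points back to an exercise intervention already described, and two 12-week programmes precede it. Usage elsewhere does not settle which is meant:

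- Section 4 uses similar words for aerobic training: "prior to and after engaging in a 12-week exercise program that has been shown repeatedly to increase oxygen metabolism".
- The remote-monitoring paragraph of section 6 uses them for participants generally, who "will be given the option to continue their exercise intervention visits remotely". It then treats those assigned to cycling as one case.

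Two readings remain:

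- *Delayed start.* Wait-listed people later enter aerobic or stretching. This agrees with the two-way randomisation and with 2 x 20. Only the size of the delayed subset and its balance across arms are missing.
- *Third group.* The wait-list is a separate control. This agrees with its heading, but not with the either-or randomisation or with 2 x 20 = 40.

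**3. Duration, on either reading.** Inputs: 12 weeks of waiting and 12 weeks of intervention (section 6, wait-list paragraph), and a 4-month maximum (section 6, Study Visits). One month is taken as 30.44 days.

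- Wait-list path: 12 + 12 = 24 weeks = 168 days; 168 / 30.44 = 5.5 months.
- Stated maximum: 4 x 30.44 / 7 = 17.4 weeks.
- Excess: 24 - 17.4 = 6.6 weeks, before any time for assessment visits.
- Ordinary path: 17.4 - 12 = 5.4 weeks remain for assessments, so a participant who does not wait fits within 4 months.

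**4. Group size, third-group reading only (illustration).** Assumptions not in the plan: two-sample t-test, two-sided alpha .05, 8 people wait-listed, and their later data not counted in either arm. The effect size is the plan's d = .83. Power comes from the noncentral t distribution with noncentrality d x sqrt(n/2) and 2n - 2 degrees of freedom.

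- 20 per arm: .83 x sqrt(10) = 2.62, 38 df, power .73.
- 8 of 40 wait-listed: (40 - 8)/2 = 16 per arm; .83 x sqrt(8) = 2.35, 30 df, power .62.
- 8 of 48 wait-listed: (48 - 8)/2 = 20 per arm, power .73, but the whole dropout reserve is used.
- At d = 1.33, the lower end of the range that section 10 quotes for the aerobic intervention, power is .98 at 20 per arm and .95 at 16.

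Under the delayed-start reading with the delay balanced within arms, each arm keeps 20 and power does not change.

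**5. Sample timing.** If weeks are counted from enrolment, week 12 for a wait-listed person is the end of the wait, before any exercise. If they are counted from the start of the intervention, it is the end of training. Section 7 does not say which.

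**The case against.** The best defence is that there is no third arm. The wait-list paragraph sends people on to an intervention already described, which plausibly takes in both programmes and the randomisation before them. The later arm may be unnamed because it is randomised. On that view a two-arm allocation list can be written, the wait-list data are not discarded, and no power is lost. This stands as a coherent reading, but the text does not state it, and the heading given to the wait-list points the other way.

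On duration, the 4 months may mean active participation, since the wait involves no contact with the study team, and the missing visit table may have carried a wait-list entry. The table could supply a size. However, the 4-month sentence as written makes no exception, and its natural meaning conflicts with 24 weeks.

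The heading over the stretching arm may be only a slip, because the paragraph beneath it plainly describes stretching and balance work. That is fair. It matters only because the control label is then used for a different group.

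Three stronger conclusions are tempting, and the documents do not support them:

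- *That the wait-list costs the trial power.* This needs a separate group drawn from the 40, a wait-list size, an alpha, and exclusion of the wait-listed people's later data. The plan states none of these.
- *That the missing analysis role is a defect of the wait-list.* The available text states no analysis model for any arm, so this gap is general.
- *That the comparator for the exercise aims is unsettled because Aim 2 names none.* Aim 2 reads "To determine the effect of an aerobic exercise regimen on motor learning and related GABA concentration changes using MRS", but sections 3 and 6 give the contrast with stretching. Naming it again in the aims would be a drafting preference.

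**Conclusion.** The concern holds as an inconsistency that should be fixed; it does not demonstrate a flawed design. Two points are established.

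- Control names two different groups, and the wait-list has no size in the available text and no explicit place in the randomisation. Whether it is a third group or a delayed start cannot be decided from the document.
- The stated participation time is too short for every wait-listed person by at least 6.6 weeks (24 against 17.4 weeks). This needs only the plan's own figures and the ordinary meaning of the 4-month sentence.

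The fall in power from .73 to .62 is an illustration of one reading under the assumptions listed in step 4, and the conclusion does not rest on it.

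**What to change.** Reconcile the abstract, the section 6 paragraphs (Study Visits, randomisation, Interval Exercise Group, Control Group) and section 10 to one scheme, with one name for each group.

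- **Option A: delete the wait-list paragraph.** This is a wording amendment. It gives up the estimate of test-retest change without exercise. In a small subset that estimate would be imprecise anyway: with 8 people (an assumed size; 7 df), the 95% interval for the SD of change runs from 0.66 to 2.04 times the estimate.
- **Option B: keep it as a delayed start.** Randomise all older adults 1:1 to aerobic or stretching at enrolment, with the delay balanced within each arm. State how many are delayed, and count each person once towards the 20 per arm. Use the post-wait assessment as baseline for the arm comparison. Correct the Study Visits duration to at least 24 weeks plus visits for delayed starters, and state from which point weeks 1 and 12 in section 7 are counted. This needs a revised allocation list and a longer stated participation time, with no extra participants.
- **If a separate third group is truly intended:** state its size and restate the smaller per-arm size in section 10. For scale, under a two-sided alpha of .05 and 80% power (both assumed), the detectable effect rises from d = .91 at 20 per arm to d = 1.02 at 16. The duration and week-counting corrections in option B apply here too.

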Single pulse measures: Four single-pulse TMS measures will be taken: size and latency of Motor Evoked Potential (MEP) in right FDI muscle at resting motor threshold, duration of ipsilateral silent period (iSP), and MEP recruitment curves (RC). Electromyography (EMG) will be taken from the FDI muscle on both hands. Muscle activation will be monitored with a real-time oscilloscope software package (BrainSight 2.3; Rogue Research). A MagVenture x100 magnetic stimulator (MagVenture, Denmark) and a focal figure of 8 coil will be used to stimulate the left primary motor cortex during the initial mapping procedure. The coil will be placed tangential to the scalp with the handle pointing backwards and 45° away from the midline for stimulation. The scalp site corresponding to the lowest stimulator output sufficient to generate a magnetic evoked

potential of at least 50 mV in 6 out of ten trials will be defined as the area of lowest motor threshold (LMT), also known as the “hotspot”. The MEP size measure will be taken using ten stimulations of the left primary motor area FDI hotspot at LMT. The right FDI motor hotspot will be assessed using the same procedure, but with the left hand and stimulation delivered to the right motor cortex.

The ipsilateral silent period will be determined using a longstanding method (Wasserman et al. 1991). For ipsilateral silent period, the left FDI muscle will be contracted via pinch grip at 25% maximal voluntary contraction (determined by grip dynamometer) and an 80% LMT stimulus will be delivered to the left primary motor area FDI “hotspot”, previously determined by an initial sensitivity assessment. Stimulator output equivalent to 150% LMT is delivered to the left FDI hotspot. FDI recruitment curves, a measure of cortical excitability, will be generated by stimulation at the LMT hotspot over progressively increasing intensities. Testing proceeds by placing the coil at the hotspot and recording 5 stimuli in 10% increments beginning at an intensity of 10% below LMT threshold. Data collection for the RC will be terminated when a plateau of the sigmoidal curve is observed. The slope of the RC will be generated from the data using linear regression.

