Some participants will experience exercise-related injuries and possibly muscle soreness and fatigue as a result of the testing and the intervention. There is a small risk for loss of balance and injury from a fall while walking and during balance testing. However, walking and balance measurements will only be a few minutes at a time, and research personnel will be with the participant at all times. Most injuries will be selflimited, though it is possible for permanent injuries to occur, including broken bones or joint problems. There are minor risks of musculoskeletal problems associated with the performance evaluation measures of the study.

Adverse event reporting:

In the case of a reportable event, the Principal Investigator will follow the current Atlanta VA Research and Development operating procedure for reporting. This includes notifying the Emory IRB within the appropriate time period of any adverse event occurring.

All study staff will be trained on proper reporting procedures of adverse events (i.e.- contact emergency medical services for immediate medical emergency and later the Principal Investigator, if not present). [name] will notify the IRB and VA SIO of any reportable events.

8. Possible Benefits:

The major benefit of the study is the advancement of scientific knowledge about brain systems. Such knowledge may one day be used to increase the efficiency of rehabilitation techniques after brain injury, and might even have some implications for the way we teach skilled movement or other functions to neurologically normal

individuals. As a responsibility to the participants, anatomic scans will be read by a qualified physician if unexpected abnormalities arise.

9. Participant selection:

The study will recruit 40 healthy adult participants between the years of 60 and 80. The study will also recruit 20 healthy adults ages 18-35 as a comparator group for the MRI scans. Groups will be matched for gender, if possible, given that a large majority of Veterans are male.

Inclusion/Exclusion Criteria. Participants will be initially screened via phone for inclusion. The key inclusion criteria and final participant pool will consist of right handed English speaking individuals. All participants will be strongly right-handed (Edinburgh Handedness Inventory, Oldfield, 1971). Cortical activation characteristics in primary motor cortex are altered by repeated digit movement practice (piano playing, expert typists, etc.).

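### MEP size is read at a threshold that is itself set by MEP amplitude, so it is largely anchored and could miss a real excitability change, while the threshold is not listed as an outcome

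*Combined protocol and SAP*

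**What the plan says.** All of this stands in section 6, TMS Measures, under the single-pulse measures.

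- The list of outcomes opens: "Four single-pulse TMS measures will be taken: size and latency of Motor Evoked Potential (MEP) in right FDI muscle at resting motor threshold". The other two are the duration of the ipsilateral silent period (iSP) and the recruitment curves. LMT is not on the list.
- LMT comes from an amplitude rule: the lowest stimulator output that yields an MEP of at least 50 (in the unit printed) "in 6 out of ten trials will be defined as the area of lowest motor threshold".
- MEP size is then recorded at that output: "The MEP size measure will be taken using ten stimulations of the left primary motor area FDI hotspot at LMT".
- The recruitment curve is described separately: "FDI recruitment curves, a measure of cortical excitability, will be generated by stimulation at the LMT hotspot over progressively increasing intensities". It uses five stimuli per 10% step, from 10% below LMT to the plateau, and its only named summary is a slope from linear regression.

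Section 5, Aim 3, uses TMS before and after exercise: "To determine the effects of motor learning prior to and after an aerobic exercise intervention on GABA receptor function using TMS". The documents do not say whether LMT is determined again after the intervention or whether the baseline output is carried forward.

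**The concern.** A measurement taken at an intensity chosen to make that measurement reach a set value says little about the person. If the motor cortex becomes more excitable, less output is needed to meet the 6-of-10 rule. LMT falls, and the MEP recorded at the new LMT is again just above the criterion. The information sits in LMT, which the plan treats as a set-up value.

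The study's title and purpose concern cortical excitability. A near-certain null on a listed measure could be reported as no change in excitability when a change had occurred and had been recorded elsewhere in the raw data.

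**Working it through.** **The plan's own figure.** The plan gives none for MEP size. Section 10 mentions an effect size of about .83 for the MRS and TMS measures with 20 per group, without alpha or power. It serves below only as a yardstick, and the argument does not depend on it.

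**Inputs from the plan.** Criterion 50; 6 of 10 trials; ten pulses at LMT.

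**Inputs assumed (the documents give none).** Single MEPs are lognormal with log-scale SD between 0.3 and 1.0. In the simulation the SD is 0.5 or 0.75, true thresholds have mean 50 and SD 8 (% output), and log amplitude rises by 0.12 per 1% output (SD between people 0.02).

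**Step 1: what MEP size at LMT depends on.** At an output where P(MEP ≥ 50) = 0.6, the log-median is ln 50 + 0.253·SD, so

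mean MEP at LMT = 50 · exp(0.253·SD + SD²/2).

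- SD 0.4: 50 · exp(0.101 + 0.080) = 59.9
- SD 0.6: 50 · exp(0.152 + 0.180) = 69.7
- SD 0.8: 50 · exp(0.203 + 0.320) = 84.3

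The formula contains no threshold or curve position. It contains only the criterion and the trial-to-trial spread. With P between 0.5 and 0.6 and SD from 0.3 to 1.0, the median lies between 50 and 64 and the mean between 52 and 106.

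**Step 2: pre/post change.** The stated rule was simulated in 4,000 people per scenario: output was raised in 1-point steps until 6 of 10 MEPs reached 50, then ten new pulses were averaged. The standardized change is the mean log change divided by its SD.

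| Scenario | Ratio of MEP size, post/pre | Standardized change | Change in LMT |
|---|---|---|---|
| Threshold falls 5 points, LMT set afresh | 0.99 to 1.00 | about 0 | −5.0 |
| Threshold falls 5 points, baseline output reused | 1.83 | 1.6 to 2.4 | not re-measured |
| Slope 1.5 times steeper, LMT set afresh | 1.06 to 1.07 | 0.13 to 0.17 | +0.2 to +0.5 |
| Trial SD rises from 0.5 to 0.75, LMT set afresh | 1.08 | 0.18 | not reported |

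The second row can be checked by hand: exp(0.12 × 5) = 1.82. For slopes two SDs either side, exp(0.08 × 5) = 1.49 and exp(0.16 × 5) = 2.23. The size of that contrast therefore depends on the assumed curve. The value near 1 in the first row follows from the titration.

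The last row depends on how closely the search finds the 60% point. If it were found exactly, the step 1 formula gives 80.1/64.3 = 1.25. Even then the measure would be responding to spread and not to the level of excitability.

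**Step 3: does the recruitment curve cover the gap?** Sampling starts relative to LMT. If the whole curve moves sideways along the output axis, the sampled points move with it and the slope per point of output is unchanged. If output were instead expressed as a percentage of LMT, the slope would scale with LMT: a fall from 50 to 45 multiplies it by 45/50 = 0.90, so greater excitability would appear as a shallower curve. Either way, the named summary does not report a horizontal shift as such, although the raw curve data contain it.

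**The case against.** The strongest reply is that the plan never says LMT is determined again after exercise. It speaks of an initial mapping and an initial sensitivity assessment. If the baseline output is held, MEP size can move strongly (second row of the table). This stands as a limit on the exercise claim. However, an MEP recorded at a carried-forward output is no longer at that visit's resting threshold, which is how the measure is listed, and no provision for holding the output is given. Comparisons between people at Assessment 1 are anchored either way, because each person has an individual LMT.

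A reader might infer that MEP size is fixed by construction and cannot show any difference. The documents do not support that. The rule sets a minimum count of MEPs above the criterion, so slope and trial-to-trial spread can still move the mean somewhat.

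A reader might also infer that the TMS programme, or Aim 3, fails. That does not follow. The plan attaches the excitability label to the recruitment curve, not to MEP size. Latency, iSP duration and the paired-pulse measures are not set by the amplitude criterion. The Aim 3 hypotheses concern intracortical and interhemispheric inhibition, and section 10 powers on change in MRS.

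Nor is a young-versus-old MEP comparison clearly planned: "The study will also recruit 20 healthy adults ages 18-35 as a comparator group for the MRI scans".

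Finally, every ratio above rests on assumed curves, since the plan gives no expected change in threshold. This is conceded. The anchoring itself needs only the plan's own definition of LMT.

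**Conclusion.** The point holds in a limited form. MEP size at LMT is largely anchored near the amplitude criterion that defines LMT. If LMT is set afresh at each visit, a pure threshold change leaves MEP size essentially unchanged (ratio 0.99 to 1.00), while LMT carries the whole change. Residual effects from slope or spread were 0.13 to 0.18 standardized units in the stepwise simulation, small beside the .83 named for TMS measures. A spread effect could be larger if the threshold were located more precisely. Because LMT is unlisted and the recruitment-curve slope does not register a horizontal shift, a real change could go unreported even though the data hold it.

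The conclusion assumes that LMT is re-determined, that MEP amplitudes are roughly lognormal, and that the search follows the 6-of-10 rule. It does not touch the powered endpoint. It should be corrected because a listed measure would give a near-guaranteed and misleading null.

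**What to change.** In section 6, TMS Measures, Single pulse measures:

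1. List LMT, in % stimulator output, as an outcome at Assessment 1 and Assessment 2, and state that it is re-determined at each.
2. Do not interpret MEP size at LMT as an excitability outcome. Keep the ten pulses for latency and as a check that the threshold was found correctly.
3. Take MEP size from the suprathreshold part of the recruitment curve, and compare visits at one and the same absolute output, already used for that person at Assessment 1. Fix in advance the rule for choosing that output, and how the repeated MEPs are summarised.

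The cost is protocol wording. Finding the hotspot already yields LMT, and the recruitment curve already yields suprathreshold MEPs. At most a few extra assessment pulses are needed when the chosen output does not fall on the Assessment 2 curve.
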